### **6.3.6 Pulmonary Adverse Effects**

In the event of acute onset (grade  $\geq 2$ ) or worsening pulmonary symptoms which are not thought to be related to underlying cancer, cetuximab therapy should be interrupted and a prompt investigation of these symptoms should occur. Cetuximab retreatment should not occur until these symptoms have resolved to grade 1. If interstitial lung disease is confirmed, cetuximab should be discontinued and the patient should be treated appropriately.

### **6.3.7 Renal Adverse Effects**

Hypomagnesemia has been reported with cetuximab when administered as a single agent and in combination with multiple different chemotherapeutic regimens. Patients receiving cetuximab should be monitored for hypomagnesemia. Magnesium repletion may be necessary based on clinical judgment.

## **7.0 REGULATORY AND REPORTING REQUIREMENTS**

The entities providing oversight of safety and compliance with the protocol require reporting as outlined below. Please refer to Appendix F for definitions and Appendix G for a grid of reporting timelines.

Adverse events will be tracked from the start of treatment through 30 days following the last day of study treatment. All adverse events must be recorded on the toxicity tracking case report form (CRF).

Refer to the data submission schedule in Section 12 for instructions on the collection of AEs in the EDC.

Reporting requirements for Washington University study team may be found in Section 7.1.

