### **5.3.5 Step Three Assessments**

Step Three will start 16 to 22 weeks after the completion of CRT.

1. Clinical examination Day 1 of each cycle.
2. CBC Day 1 of each cycle.
3. CMP, Mg Day 1 of each cycle.
4. EKG Day 1 of Cycles 1 and 4, and Day 29 of Cycle 6 (EOT).
5. QOL assessment at Cycle 1 Day 1, Cycle 4 Day 1, and Cycle 6 Day 29 (EOT).
6. AE assessments Day 1 of each cycle.
7. Study Lab collection of 3 green top tubes for PBMC at C1D22.
8. Thirty to 45 days after final cycle of adjuvant palbociclib, there will be a clinical examination, CBC, CMP, EKG, and AE assessment.

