## **5.4 Toxicity and Response Evaluations**

All patients who receive any study treatment are evaluable for toxicity. Patients are evaluated from first receiving study treatment until a 30-day follow up after the conclusion of treatment or death.

All patients are evaluable for disease response unless they discontinue treatment due to adverse event(s), patient withdrawal, or early death prior to completion of the disease

assessment at the end of Step 1(neoadjuvant treatment) and have not had any disease assessment.

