## **5.6 Women of Childbearing Potential**

Women of childbearing potential (defined as women with regular menses, women with amenorrhea, women with irregular cycles, women using a contraceptive method that precludes withdrawal bleeding, and women who have had a tubal ligation) are required to have a negative serum pregnancy test within 28 days prior to the first dose of palbociclib.

Female and male patients (along with their female partners) are required to use two forms of acceptable contraception, including one barrier method, during participation in the study and for 3 months following the last dose of palbociclib.

If a patient is suspected to be pregnant, all study drugs should be immediately discontinued. In addition, a positive urine test must be confirmed by a serum pregnancy test. If it is confirmed that the patient is not pregnant, the patient may resume dosing.

If a female patient or female partner of a male patient becomes pregnant during therapy or within 28 days after the last dose of palbociclib, the investigator must be notified in order to facilitate outcome follow-up.

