## **5.8 Duration of Follow-up**

Patients will have follow-up visits after the end of treatment at 30-45 days, and will also have visits at 8 months after end of CRT, 12 months after end of CRT, and every 6 months thereafter until 5 years have elapsed since the end of treatment. Patients removed from study for unacceptable adverse events will be followed until resolution or stabilization of the adverse event.

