### **7.1.3 Reporting to Pfizer**

Within 24 hours of first awareness of the event (immediately if the event is fatal or life-threatening), the PI or designee will report to Pfizer by facsimile any serious adverse drug experience (as defined in Appendix F) that occurs during the SAE reporting period (as defined in Section 7.0) in a study subject receiving palbociclib. Such SAEs will be reported using MedWatch form and the Pfizer Reportable Event Fax Cover Sheet (Appendix C) should also be included. SAEs should be reported as soon as they are determined to meet the definition, even if complete information is not yet available.

Even though there may not be an associated SAE, exposure to palbociclib during pregnancy or lactation is reportable. In addition, occupational exposure to palbociclib is reportable, and a lack of effect of palbociclib may also be reportable.

Hy's Law Cases: Cases of potential drug-induced liver injury as assessed by laboratory test values ("Hy's Law Cases") are also reportable to Pfizer. If a study subject develops abnormal values in aspartate transaminase (AST) or alanine transaminase (ALT) or both, concurrent with abnormal elevations in total bilirubin and no other known cause of liver injury, that event would be classified as a Hy's Law Case.

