8. C1D1, C4D1, C6D29
9. Starting 16-22 weeks post CRT
10. 30-45 days after final cycle of adjuvant palbociclib
11. +/- 1 month
12. After completion of CRT
13. To be collected at Step 3 Cycle 1 D22 and at 4 months post Step 3 (see protocol section 9.2)

14. Laryngoscopy (FOE) will be conducted as standard of care after 12 months of follow-up, so they will occur at some, but not all, of the long-term follow-up visits

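### AE and manufacturer-SAE tracking stops at 30 days although the last safety visit falls at 30-45 days, and pregnancy notification stops at 28 days against a 3-month contraception requirement

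*Combined protocol and SAP*

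**What the plan says.** **Adverse events.** Section 7.0 sets the tracking period: "Adverse events will be tracked from the start of treatment through 30 days following the last day of study treatment". Section 7.1.3 makes serious events reportable to the manufacturer when the event is one "that occurs during the SAE reporting period (as defined in Section 7.0"), so the same end date governs those reports. Section 5.4 evaluates patients for toxicity "until a 30-day follow up after the conclusion of treatment or death". Section 12.1, to which 7.0 refers for AE collection, requires capture from the start of treatment and names no end.

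**The last safety visit.** Section 5.3.5 says: "Thirty to 45 days after final cycle of adjuvant palbociclib, there will be a clinical examination, CBC, CMP, EKG, and AE assessment". Footnote 10 of the Section 10.2 calendar agrees: "30-45 days after final cycle of adjuvant palbociclib". Section 5.8 uses a different starting point: "Patients will have follow-up visits after the end of treatment at 30-45 days". Section 5.2.1 gives palbociclib on Days 1-21 of each 28-day cycle, and 5.3.5 labels Cycle 6 Day 29 as end of treatment (EOT).

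**Pregnancy.** Section 5.6 requires contraception, for male patients and their female partners as well as for women, "during participation in the study and for 3 months following the last dose of palbociclib". Inclusion criterion 7 and exclusion criterion 12 give 90 days after treatment is completed. The notification duty in 5.6 is shorter: if a patient or partner "becomes pregnant during therapy or within 28 days after the last dose of palbociclib, the investigator must be notified".

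**The concern.** The protocol schedules a final examination, laboratory tests, EKG and AE assessment, yet on most readings it places them after the date on which the AE and SAE period ends. A new abnormality found at that visit then has no clear status. Under 7.0 it is outside the period, under 12.1 it must be captured, and under 7.1.3 it need not go to the manufacturer even if serious. Because the sections count from different points (last day of treatment, conclusion of treatment, end of treatment, final cycle), study staff could apply different cut-offs to different patients.

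The pregnancy periods have the same kind of mismatch. Section 5.6 asks for contraception for 3 months but asks to be told of a pregnancy, for outcome follow-up, during only the first 28 days after the last dose. At stake are the completeness of the safety data and the consistency of reporting. No efficacy result depends on it.

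**Working it through.** The plan gives no figure of its own to reproduce. The check is day arithmetic on its stated windows, with Cycle 6 Day 1 as day 1.

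**Inputs**
- Last planned dose: day 21; end of cycle: day 28 (5.2.1).
- EOT visit: day 29 (5.3.5).
- AE/SAE window: anchor + 30 days (7.0, 7.1.3).
- Safety visit: anchor + 30 to anchor + 45 days, which is 16 permitted days (5.3.5, 5.8, calendar footnote 10).

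**Formulas**
- Window closes on day A + 30, where A is the anchor for the window.
- Visit runs from day V + 30 to day V + 45, where V is the anchor for the visit.
- Gap = visit day minus closing day. A visit day is inside the window if the gap is 0 or less.

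| Window from (A) | Closes | Visit from (V) | Visit days | Gap | Visit days inside |
|---|---|---|---|---|---|
| last dose, 21 | 51 | cycle end, 28 | 58-73 | 7 to 22 | 0 of 16 |
| last dose, 21 | 51 | EOT, 29 | 59-74 | 8 to 23 | 0 of 16 |
| last dose, 21 | 51 | last dose, 21 | 51-66 | 0 to 15 | 1 of 16 |
| cycle end, 28 | 58 | cycle end, 28 | 58-73 | 0 to 15 | 1 of 16 |
| EOT, 29 | 59 | EOT, 29 | 59-74 | 0 to 15 | 1 of 16 |
| cycle end, 28 | 58 | EOT, 29 | 59-74 | 1 to 16 | 0 of 16 |
| EOT, 29 | 59 | cycle end, 28 | 58-73 | -1 to 14 | 2 of 16 |
| cycle end, 28 | 58 | last dose, 21 | 51-66 | -7 to 8 | 8 of 16 |
| EOT, 29 | 59 | last dose, 21 | 51-66 | -8 to 7 | 9 of 16 |

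The first row follows the wording most closely: the last day of treatment is the last dose, and the visit is counted from the final 28-day cycle. The three shared-anchor rows all give 0 to 15. Only the last two rows put about half the visit days inside. They start the window later than the visit clock, which does not fit 5.3.5 or footnote 10, where the visit is counted from the final cycle.

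**Onset and detection.** In Step Three, AE assessments fall on Day 1 of each cycle (5.3.5). The next one listed after Cycle 6 Day 1 is the 30-45 day visit. Events with onset between Cycle 6 Day 1 and closure are therefore collected at that visit and lie inside the period. The events left out are those with onset between closure and the visit.

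**Pregnancy.** Taking 3 months as the 90 days of inclusion 7 and exclusion 12: 90 - 28 = 62 days without the 5.6 notification duty, and 62/90 = 0.69.

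**The case against.** **A visit at or after day 30 is a normal way to close a 30-day window.** This stands in part. Section 7.0 limits the tracking period; it does not bar recording an earlier event at a later visit. A reader might infer that the last visit can add no new events to the safety data. The documents do not support that, because the visit is the collection point for everything that began after Cycle 6 Day 1 and before closure.

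**The 7-22 day gap depends on the anchor.** This also stands. Section 5.8 counts from end of treatment and 5.3.5 labels Day 29 as EOT. With a shared anchor the gap is 0-15 days, and a visit on exactly day 30 is inside.

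**Other text may keep collection open.** Section 5.4 can be read as running to the follow-up visit itself, and 12.1 states no end. FDA and HRPO reporting (7.1.4, Appendix G) does not borrow the 30-day limit; only the manufacturer report does. So the documents disagree with one another, and it would be too strong to say that all collection plainly stops. Section 5.8 follows patients removed for unacceptable adverse events until resolution or stabilization, but that covers existing events, not new ones.

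**Patients who become pregnant are partly covered elsewhere.** Inclusion 7 tells a woman to inform her physician of a pregnancy during participation, and 7.1.3 makes exposure in pregnancy reportable with no stated time limit. It would therefore be wrong to say that nothing applies to patients after day 28. Neither provision sets a duty for the female partners of male patients from day 29 to day 90.

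**A reader might go further and call the single baseline pregnancy test an error**, since palbociclib restarts in Step Three. Section 5.6 ties the test to the first dose and the calendars follow it. No text is contradicted, and a repeat test would be a clinical monitoring choice outside this point.

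**Conclusion.** Two mismatches hold.

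1. The AE and manufacturer-SAE period ends before the final safety visit, or on its first permitted day, under the closest reading and under every shared-anchor reading. The gap is 7-22 days with the window from last dose and the visit from cycle end, and 0-15 days with one anchor. What falls outside is events with onset after closure, including abnormalities first seen at the visit. The open-ended instruction in 12.1 conflicts with 7.0 and does not settle the matter.

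2. About 62 of the 90 days of required contraception (69%) carry no duty under 5.6 to notify the investigator of a pregnancy. The gap is clearest for partners.

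This assumes six completed adjuvant cycles with the last dose on Day 21, and 3 months taken as 90 days. The text of Section 8.1.9 available to me is incomplete, so the pregnancy point rests on the two periods inside 5.6 and not on any claim about 8.1.9. The primary endpoint, power and type I error are not affected. This is an inexpensive correction worth making, not a threat to the trial's conclusions.

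**What to change.** - Reconcile 5.3.5, 5.4, 5.8, 7.0, 7.1.3 and 12.1 on one named anchor, and give 12.1 the same end date as 7.0.
- Define the AE/SAE period as running through the later of 30 days after the last study treatment or the post-treatment safety visit. Section 7.1.3 then inherits this through its cross-reference to 7.0.
- In 5.6, reconcile the two periods so that notification of a pregnancy, in a patient or a partner, covers the same period as the contraception requirement, and state whether that period counts from the last dose or from completion of treatment.

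The cost is protocol wording and a few more adverse events and pregnancies to record and report. No visit, test or analysis is added.

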## **5.3 Study Procedures**

### **5.3.1 Baseline Assessment**

1. Office fiberoptic endoscopy (FOE) or operative room (OR) microlaryngoscopy (mDLx) to document the size and extent of the primary tumor site (PTS) along with research and routine biopsies of the PTS. Core or excisional biopsies of the involved neck nodes is an alternative approach to obtain tumor tissue.
2. p16INK4a IHC stain on all patients. HPV-HR (16,18) ISH will be required on all patients with p16INK4a positive oral cavity, larynx, and hypopharynx SCC.
3. Clinical examination with ECOG PS.
4. Weight.
5. Documentation of presence of PEG tube or tracheostomy tube
6. QOL assessment
7. CBC, CMP, Mg, PT/INR, PTT, pregnancy test (if woman of childbearing potential)

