#### **9.1.1 Collection of Specimens**

Tumor tissue will be collected at baseline and then after two cycles of neoadjuvant palbociclib monotherapy (conclusion of Step One). It should be collected from the primary tumor site if possible, but involved neck nodal tumor tissue is an alternative. If possible, the same site should be biopsied at baseline and end of C2.

The biopsy should consist of a minimum of 4 needle cores (14-18 gauge is preferred) if neck nodal tissue or 2 small (each 4 x 4 x4 mm) pieces of tumor if primary tumor site tissue.

If the patient has been previously enrolled in Washington University's TAP protocol (head and neck bank, HRPO #201102323), tissue that has been banked may be accessed in lieu of fresh biopsy at baseline.

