## 10.0 STUDY CALENDAR

### 10.1 Induction Palbociclib Monotherapy – Step One

	Baseline 	Step 1 – Cycle 1				Step 1 – Cycle 2				Definitive Chemotherapy/Radiation
		D1	D8	D15	D22	D1	D8	D15	D22	
Palbociclib administration 		X 	X 	X 		X 	X 	X 		
PE w/ECOG PS	X	X		X	X	X			X	
CBC	X	X	X	X	X	X	X	X	X	
CMP + magnesium	X									
PT/INR, PTT	X									
Neck CT w/contrast	X								X 	
FDG-PET/CT	X									
Laryngoscopy w/biopsy 	X									X
EKG	X					X				
Pregnancy test 	X									
FACT-H&N, EORTC QLQ-C30	X								X	
Blood for genomic sequencing	X			X				X		
Rad Tx Planning					X					See Study Calendar 2
Primary Site Photographs	X								X	

1. Palbociclib po 125 mg/day, Days 1-21 of a 28 day cycle.

2. Tumor biopsy specimens (punch, incisional or core needle) will be obtained from PTS or neck nodes. P16 to be tested by IHC and/or HPV-HR ISH at baseline only. Assessment of primary tumor site will be done by laryngoscopy performed in the office or operating room. If the patient has been previously enrolled in Washington University's TAP protocol (head and neck bank, HRPO #201102323), tissue that has been banked may be accessed in lieu of fresh biopsy at baseline.

3. In women of childbearing potential only.

4. Baseline assessments must take place no more than 28 days prior to enrollment.

5. To occur anytime post treatment D21-D25 (for M, 26 for W and 27 for Th patients).

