## 12.1 Adverse Event Collection in the Case Report Forms

All adverse events that occur beginning with start of treatment must be captured in the Toxicity Form.

Participant death due to disease progression should be reported on the Toxicity Form as grade 5 disease progression. If death is due to an AE (e.g. cardiac disorders: cardiac arrest),

report as a grade 5 event under that AE. Participant death must also be recorded on the Death Form.

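### Adverse-event collection opens at first treatment, so complications of a fresh baseline research biopsy before Day 1 are not required on the Toxicity Form

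*Combined protocol and SAP*

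**What the plan says.** Three sections set the start of adverse-event collection, and they agree.

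- Section 7.0: "Adverse events will be tracked from the start of treatment through 30 days following the last day of study treatment".
- Section 12.1: "All adverse events that occur beginning with start of treatment must be captured in the Toxicity Form".
- Section 5.4, on who is followed for toxicity and for how long: "Patients are evaluated from first receiving study treatment until a 30-day follow up after the conclusion of treatment or death".

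The research biopsy has its own schedule. Section 5.3.1 lists, at baseline, an office endoscopy or operating-room microlaryngoscopy "along with research and routine biopsies of the PTS", with core or excisional neck-node biopsy as the alternative. Section 9.1.1 gives the two time points: "Tumor tissue will be collected at baseline and then after two cycles of neoadjuvant palbociclib monotherapy (conclusion of Step One". It also gives the amount of tissue. For nodes, "The biopsy should consist of a minimum of 4 needle cores (14-18 gauge is preferred) if neck nodal tissue"; for the primary site, two pieces of about 4 mm in each dimension. Footnote 4 of the Step One calendar (Section 10.1) sets the baseline period: "Baseline assessments must take place no more than 28 days prior to enrollment".

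**The concern.** Tissue taken for research, in addition to routine tissue, carries some procedural risk. The plan schedules it twice but opens the safety record between the two occasions. A complication of the second biopsy goes on the Toxicity Form. The same complication of the first, if it occurs before Day 1, does not have to. The documents give no reason for treating the two differently.

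At stake is how complete the trial's own safety data are for a procedure that mainly serves exploratory objectives (Sections 2.3 and 9.1). In a trial of 24 patients, a single serious procedural complication would matter to anyone judging whether the tissue collection was acceptable.

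**Working it through.** The plan states no figure that can be reproduced here, so the check sets the sections side by side.

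**1. When the window opens.** Sections 5.4, 7.0 and 12.1 all start at first study treatment, which is Day 1 of palbociclib. No section opens collection earlier for any class of event.

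**2. When the baseline biopsy happens.** It is a baseline procedure (Sections 5.3.1 and 9.1.1), done up to 28 days before enrollment (Section 10.1, footnote 4). The uncovered interval runs from the biopsy to the first dose. It can last up to 28 days plus the time from enrollment to Day 1, which the documents do not state.

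**3. When the second biopsy happens.** Section 5.3.2 puts it at Cycle 2 Days 18–22. That is after the first dose and before the window closes.

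**4. The same event, two outcomes.**

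| Event | Before first dose? | Required on the Toxicity Form? |
|---|---|---|
| Bleed after a fresh baseline research biopsy, before Day 1 | Yes | No |
| Bleed after the end-of-Step-One biopsy | No | Yes |

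**5. What follows downstream.** Under Appendix G, the toxicity table in the DSM report carries adverse events to QASMC, and the current version goes to FDA with the IND annual report. An event not required on the form need not appear there. Section 5.4 also counts as evaluable for toxicity only patients who receive study treatment. A patient whose biopsy complication prevented Day 1 would therefore not be in that group.

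**6. How many biopsies.** Section 14.4 plans 24 patients. Two biopsies each gives 24 × 2 = 48, of which 24 come before Day 1: 24 / 48 = 50%. This is a ceiling among enrolled patients. Section 9.1.1 allows banked tissue in place of a fresh baseline biopsy, and Section 9.1 allows a biopsy to be omitted for financial or safety reasons. The documents do not say how often either will happen.

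The documents give no complication rate for the biopsy, so no expected number of events is calculated.

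**The case against.** The strongest reply has four parts.

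*Other routes exist.* A reader might infer that these complications are never recorded, or leave no safety record at all. The documents do not support that. Section 11.0 sends adverse events that the investigator or coordinator learns of to HRPO and QASMC under institutional guidelines, with no start date. Section 7.1.2 and Appendix G do the same for unanticipated problems, whatever the treatment day. Appendix G also provides for summary reporting of other events to HRPO at continuing review. The institutional rules are not in the documents, so how many biopsy events these routes would catch is unknown. This part stands, but it concerns oversight reporting. None of these routes requires an entry on the Toxicity Form, and an expected complication such as bleeding may not qualify as unanticipated.

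*The window fits the definition.* Appendix F defines an adverse event as one associated with use of a drug, so opening at first dose is coherent. This also stands: the sections do not contradict one another. The gap is a design choice that can be improved. Nor is there a gap in reporting to the drug supplier. Section 7.1.3 covers serious adverse drug experiences, and only those "that occurs during the SAE reporting period (as defined in Section 7.0) in a study subject receiving palbociclib". A biopsy event before any palbociclib lies outside that duty by its own terms.

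*The research share of the risk is smaller than it looks.* Research and routine biopsies may be taken at the same endoscopy, which also documents tumor extent. Part of the procedural risk would then arise anyway, and the research biopsy can be replaced or omitted. This limits the size of the concern but does not remove it for patients who do have a fresh research biopsy.

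*No planned result changes.* A reader might infer that the reported biopsy risk will be too low. No objective, endpoint or analysis in Sections 2 or 14 reports a biopsy complication rate, so there is no such estimate to bias. The continuous safety rule in Section 14.7 counts palbociclib-related delay in starting chemoradiation after Cycle 2 Day 28 and is untouched. This part stands in full.

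**Conclusion.** The concern holds in a limited form. As Sections 5.4, 7.0 and 12.1 are written, a complication of a fresh baseline research biopsy that occurs before Day 1 is not required on the Toxicity Form and need not enter the toxicity tables, while the same complication of the later biopsy is captured.

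The size is at most 24 of 48 planned biopsies among enrolled patients, and possibly fewer. This rests on two readings: that start of treatment means the first palbociclib dose, and that no institutional rule outside these documents requires such events on the trial's own forms.

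The effect is on the completeness of safety data for a research procedure. The primary and secondary analyses and the safety rule are unaffected. The change is worth making because it is cheap and specific.

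**What to change.** In Sections 5.4, 7.0 and 12.1, add that adverse events and serious adverse events related to a protocol-required research procedure are collected from the time of the first such procedure. Keep collection of all adverse events from first treatment as it is. Say explicitly that these procedure-related events count although no drug has yet been given, since the Appendix F definition refers to drug use.

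Add research biopsy as an attribution choice on the Toxicity Form, so that events after either biopsy can be identified.

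Section 7.1.3 takes its reporting period from Section 7.0. When 7.0 is amended, confirm that 7.1.3 stays limited to subjects receiving palbociclib, so that no unintended supplier-reporting duty is created.

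The cost is a small wording amendment, one added form choice and a few more adverse-event records. Treatment, endpoints, sample size and analyses do not change.
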